**QUX 16-004, Learn, Engage, Act, Process (LEAP) for Personalized Weight Management Support (QUE
15-286)**

NCT02825680

Study Protocol and Statistical Analysis Plan

September 15, 2020

This study was conducted as a pragmatic stepped-wedge clustered randomized controlled trial designed as a non-research quality improvement initiative primarily to improve the quality of preventive services in the VA as part of an ongoing partnership with the VA National Center for Health Promotion and Disease Prevention (see letter from [name], MPH; Chief Consultant for Preventive Medicine). Given the non-research quality improvement designation, this study did not have a protocol reviewed by an Institutional Review Board, but the following is an excerpt from the study proposal which was peer reviewed and approved for funding in June 2015 as part of a VA Quality Enhancement Research Initiative field program at the VA Ann Arbor Healthcare System (aka PROVE QUERI). This document provides an excerpt from the nationally reviewed proposal that describes the study aims, procedures, design, and analysis plan for this trial.

For more details on study design and analysis, please visit:

https://bookdown.org/[name]/leap_reach_analysis/

Excerpt from PROVE QUERI Program Proposal:

Project #2:

Learn. Engage. Act. Program (LEAP) for Personalized Weight Management Support

1.0 Specific Aims

Obesity and associated health conditions cause significant burden for Veterans, 78% of whom are overweight or obese. Treatment of overweight/obesity is a high priority for VHA as part of personalized, proactive, Veteran-driven care, outlined in the Blueprint for Excellence (BPE). The VA/DoD clinical practice guidelines (CPGs) for weight management recommend comprehensive lifestyle intervention (at least 12 sessions in 12 months) as the foundation of treatment for overweight/obesity.¹³⁹

The MOVE![®] weight management program was first disseminated in January 2006 through VHA's National Center for Health Promotion and Disease Prevention (NCP)¹⁴⁰ and is one of the largest scale integrated weight management programs in the world. Several evaluations of the MOVE! program have shown significant, though modest, weight loss for participants¹⁴¹⁻¹⁴³ and reduced incidence of diabetes.¹⁴⁴ This is laudable, given the challenges in losing weight that face this population.^{141,142,145-147} Personalized coaching combined with high group cohesion among participants appear to consistently result in significantly longer engagement and higher weight loss.^{141,148} NCP recently disseminated revised guidelines for in-person group delivery of MOVE! (hereafter, referred to as **New MOVE!**), which is the cornerstone of the family of MOVE! weight management programs available to Veterans. **New MOVE!** has been redesigned to align with the new CPGs and formative findings from the VA Diabetes Prevention Program (DPP) Clinical Demonstration Project.¹⁴⁸ Implementation of **New MOVE!** is expected to increase Veteran engagement and outcomes through greater treatment intensity, stronger group cohesion, and a single consistent coach transitioning to a more personalized style of delivery using patient-centered coaching skills.

NCP has a long history of providing program support to local MOVE! teams tasked with delivering MOVE!, and now with implementing **New MOVE!**, through monthly phone calls, quarterly education sessions and *ad hoc* technical assistance. Despite this, local programs often do not align with CPGs; they vary widely in the number of sessions offered and other key characteristics,^{101,149} often because of local organizational barriers.^{100,101,150} Providing more intensive systems redesign and implementation support to help local teams mitigate these barriers will help increase fidelity to **New MOVE!**. Higher fidelity to **New MOVE!** will improve weight outcomes,^{151,152} and a more effective program will help increase Veteran participation and continued engagement. This project will compare an enhanced form of NCP support plus the "Learn. Engage. Act. Program" (LEAP) versus enhanced NCP support alone.

Aim 1: To develop three core products to enhance NCP support to VAMCs and to pilot LEAP in three VAMCs.

H1: Dissemination of products to enhance NCP support will improve MOVE! outcomes.

Aim 2: To determine effectiveness of LEAP plus enhanced NCP support (LEAP+NCP) versus enhanced NCP support alone.

H2: VAMCs with LEAP+NCP will have better MOVE! group outcomes than VAMCs with enhanced NCP support alone.

Aim 3: To conduct formative and cost evaluations to refine design of LEAP and inform future scaling-up of LEAP.

2.0 Rationale

Since its inception in 2006, MOVE! has enjoyed relative success. However, the high burden of overweight/obesity in VHA creates an urgency to strive for greater improvements in MOVE! effectiveness with respect to system-wide outcomes and to decrease the high variation in MOVE! program characteristics and outcomes across VAMCs. VAMCs report high annual rates (95%)^{143,153} of obesity screening and brief counseling,¹⁵³ which presents a key opportunity to engage Veteran who are candidates for MOVE!. Although VHA compares quite favorably in rates of individuals who initiate participation in a weight loss program – less than 6% initiate participation in weight loss programs in the general population,¹⁵⁴ while 10-12%¹⁴³ of MOVE! candidate Veterans do so – there is room for improvement.

Figure 4: Aggregate FY2014 MOVE! Group Visits per 100 Overweight/Obese Veterans Enrolled in Primary Care by VAMC

[figure not shown]

Figure 4 shows the wide variation in MOVE! group visit rates across VAMCs in FY2014. The highest-ranked VAMC reported more than 70 MOVE! group visits per 100 candidate Veterans. However, several VAMCs appear not to have a viable MOVE! group program, reporting fewer than 10 visits. One reason for high variation in aggregate visits may be variation in local organizational barriers. Our earlier work with three different lifestyle programs (MOVE!, TeleMOVE, and the Telephone Lifestyle Coaching (TLC) program) consistently revealed high variation in the

presence of key organizational barriers, which affects viability of MOVE! group programming. In a recent NCP call with 79 MOVE! Coordinators, **99% expressed willingness to participate in a program aimed at providing more intensive support to implement *New MOVE!*. This dramatically high level of interest speaks to the strong need for additional support to assist with implementation.**

Our primary outcome of interest is the aggregate number of visits for MOVE! candidates who live within 40 miles of their VAMC. This outcome can be improved by increasing the number of participants who complete at least one session and/or increasing the number of sessions completed by each participant. Improved group cohesion, a stronger relationship with a consistent coach, more personalized coaching, and opportunities to attend more sessions should increase these numbers, which will lead to better weight outcomes.¹⁵⁵ Furthermore, engaging more Veterans in MOVE! will help VHA “transition from sick care to health care in the broadest sense” through more “personalized, proactive and patient-driven care that inspires Veterans to their highest possible level of health and well-being” (BPE Strategy 6).

3.0 Procedures

As described in our Implementation Core*, three core products will be developed in Year 1: 1) a Construct Assessment Tool; 2) a Barrier Busters Tool; and 3) a Program Intelligence Portal (Portal). These products will be made available online for use by MOVE! teams in all VHA facilities. Much of the work has already been done on the Construct Assessment and Barrier Busters Tools. Most of our tool development effort in the first year will be devoted to developing the Portal, which will draw on advanced methods for visually displaying data in a way that has meaning for local teams. For example, users might be interested in seeing geographic displays (e.g., choropleth maps) to visually display where MOVE! participants are coming from compared to non-participants, or longitudinal graphs of engagement and weight outcomes over time. In partnership with OABI, our team will develop a Portal for MOVE! that utilizes next-generation analytic and data visualization tools (e.g., Pyramid Analytics)¹⁵⁶ available through the VA eQuality Measures (eQM) platform. The Portal will be developed using principles of user-centered design that will help to ensure it truly meets the needs of local teams.¹⁵⁷⁻¹⁵⁹ Each of the three products developed in the first year have been specifically chosen to address high-priority gaps. ***In fact, NCP is so eager to embrace these tools we are making them available online to all sites in Year 2*** and will evaluate their effectiveness via interrupted time-series analyses (described below).

Posting products online is likely to achieve only incremental benefits, because local or individual constraints will preclude accessing and using them effectively. Thus, LEAP will be employed to provide intensive support using methods that make it feasible for scaling up to all sites; in fact, we plan to randomize 48 sites (plus three pilot sites) through the course of the project (see Figure 5 below), with the remaining sites acting as controls.

LEAP, as described in the Implementation Core, will be adapted to work with VAMC teams to implement *New MOVE!*. Findings from prior work with a quality collaborative revealed the importance of open communication, relationship building, methods training, monitoring performance, and facilitating team-

based problem-solving.⁹² Three VAMCs, one from each performance tertile, will participate in a pilot of LEAP in Y1Q4. In Years 2-3, teams from six VAMCs will participate in LEAP each quarter as described below. When LEAP was described (including the level of commitment required) in a national call, hosted by NCP in May 2015 with all MOVE! coordinators, **99% of 79 participants said “Yes” they would be willing to participate.**

3.1 Study Design

Our goal is to evaluate outcomes for all VAMCs nationwide. For Aim 1, because our NCP partners want to quickly disseminate the core products by posting them online and providing short orientations on national calls, we will use an interrupted time series analysis to assess primary, secondary, and tertiary outcomes before and after dissemination of the products among sites who do not participate in LEAP. Outcome assessments will rely on administrative data available through the Corporate Data Warehouse (CDW). Our team has extensive experience working with MOVE! program data and linking to other utilization and diagnosis data.^{141,142,145-147}

For Aim 2, in years 2-3 we will randomly assign sites to LEAP, six sites at a time. At the beginning of each quarter, sites not included in the pilot and not randomized in previous quarters will be characterized by tertile of performance with respect to aggregate visits (our primary implementation outcome). Two sites will be randomly selected from each tertile of performance to initiate LEAP.

Thus, each cohort of sites will comprise two high performing sites (a key “ingredient” for the LEAP sessions), two “learner sites” and two sites that have moderate performance. This will provide a forum where the more successful sites can “mentor” sites who are further behind. By the end of FY18, 48 sites will have participated in LEAP, plus three pilot sites in FY16. The final three months of follow-up for the last cohort will occur in FY19Q1.

[figure not shown]
3.2 Key Variables & Analyses

The primary outcome will be VAMC-level aggregated number of MOVE! visits accrued within a six-month analysis period among candidates for MOVE! who live within 40 miles of the VAMC: an implementation outcome with respect to reach.¹⁶⁰ The secondary outcome will be average percentage weight loss by patients at each VAMC at six months after a baseline MOVE! visit. Tertiary outcomes will include: 1) the proportion of patients who have at least 12 MOVE! visits within 12 months (a specified goal in the new CPGs); and 2) the proportion of patients who achieved at least 5% weight loss at six months.

For Aim 1, in addition to developing the three core products, we will evaluate their impact after they are disseminated to VAMCs in FY17 through interrupted time series analyses using administrative program data. Data prior to launch of these products (FY17 Q1) will provide “before” data. “After” data will come from sites not randomized to receive the more intensive intervention (see Aim 2) and up to the randomization time for sites randomized to LEAP. Analytic models will be similar to that of Aim 2, except the primary exposure variable will be an indicator for the period after dissemination of the three core products .

To determine effectiveness of LEAP (Aim 2), we will use a generalized linear mixed-effects model with visit counts and log link for primary outcome, percent weight loss for secondary outcome, and whether at least 12 visits in 12 months were made (1/0) and logit link for tertiary outcomes. Each model will include site as random intercepts and two indicators for tertiles as fixed effects. The primary exposure variable will be the binary time-dependent exposure variable indicating the intervention quarter for the site, i.e., a variable indicating the quarter at or beyond when the site is randomized to initiate LEAP. For each outcome, the

Figure 5: Project Activities and Stepped-wedge Trial Design

Key: Gray = Participation in Learn. Engage. Act. Program (LEAP)

parameter estimate of this exposure variable will allow testing for the effectiveness of LEAP and summarize the LEAP effect expressed as rate ratio for primary outcome, difference in percent weight change for secondary outcome, and odds ratio for tertiary outcome. The model can include other variables (e.g., quarter and participant covariates).

Power considerations. Across all sites, there will be about 22,080 MOVE! participants (20 participants per closed MOVE! cohort X 1 cohort per quarter X 8 quarters X 147 sites, with 48 sites randomized in steps to LEAP and 99 not randomized). Our previous work showed an average of 4 visits during the 6 months of follow-up and 6% completing at least 8 visits.¹⁴² We assume the minimum detectable and meaningful difference in rates during LEAP in comparison to the control period to be 7 vs. 5 visits (corresponding to a rate ratio of 1.4 and assuming a bit higher rate in control group than the number observed in the preliminary data due to implementation of tools across all sites) and percent of patients with at least 12 visits in 12 months as 10% vs. 7% (corresponding to an odds ratio of 1.48). For power considerations, the design assumes randomization of 6 sites (2 sites per tertile) to LEAP every quarter over 8 quarters starting at Q1 of FY17, and one unexposed quarter, while 3 sites are piloted (Q4 of FY16), no differential effect of LEAP across the tertiles, that 48 sites will be randomized to LEAP (rather than all VAMCs), and a within-site correlation of 0.1. The proposed design will have 99% power to detect the odds ratio of 1.4 or higher and 91% power to detect an odds ratio of 1.48 or higher with a two-sided 0.05 test.

For Aim 3, qualitative data from multiple sources will be collected, coded, and analyzed by our experienced team using documented rigorous approaches. An implementation-focused evaluation¹⁶¹ will be conducted to understand implementation processes at local facilities and to refine the content and style of the LEAP sessions. Sessions will be audio recorded (with permission from the group) and transcribed. Information related to the ERIC strategies^{83,91} used, CFIR constructs⁷⁵ mentioned as barriers or facilitators, and adaptations to *New MOVE!* will be coded and tracked along with themes related to processes and stories of implementation efforts – especially as they intersect with support through LEAP. A post-implementation interpretive evaluation¹⁶¹ will be conducted based on qualitative data collected through telephone interviews with 5-10 stakeholders (including MOVE! coordinators, Health Promotion and Disease Prevention Manager, Health Behavior Coordinator, MOVE! physician champion, Director of Primary Care, possibly a Computer Applications Coordinator, and/or quality manager) at 12 sites, half of whom participated in LEAP and half of whom did not, in FY2018-19. We will also conduct site visits to 12 other sites during this same time period. Micro costing analyses will be conducted using time logs kept by LEAP workshop facilitators and estimates of time spent by local teams. We will use approaches documented in our cost evaluation of the VA DPP program.¹⁶²

Key covariates. NCP will administer surveys at least twice (annually if allowed by VACO policy) to facility MOVE! coordinators that will include measures of context based on CFIR constructs, adaptations of *New MOVE!*, and program fidelity by eliciting key program characteristics (e.g., length). Additional covariates will include facility complexity, urban versus rural, participation in another concurrent study related to MOVE!, and proportions of Veterans in populations of interest, including but not limited to racial minorities, OEF/OIF Veterans, and women. Additionally, we will track VAMC team “engagement,” e.g., through website metrics that will track use of the core products by user account, attendance at the LEAN workshops, etc.

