4.0 Impact

Published evidence highlights that more sessions attended in evidence-based weight loss programs are strongly associated with more weight loss. By the end of the project, through incremental improvements expected by making the user-designed Portal available with the other enhancements to NCP support and even more significantly, through improvements expected in the 51 facilities participating in LEAP, we anticipate a 20% improvement in the aggregate visit rates for MOVE! group and a 10% improvement in weight outcomes. In addition, specifications for reporting data through the Portal will be given to OABI. Our methods for developing program metrics (user-based design) and the highly scalable LEAP approach to program implementation can be applied to programs other than MOVE!.

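### The primary outcome is defined as a raw VAMC visit count with no candidate denominator or offset, although other sections speak of rates; the tertiles inherit the ambiguity, and changes in the candidate pool enter the estimate

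*Combined protocol and SAP*

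**What the plan says.** The endpoint is given twice as a number. Section 2.0 has "Our primary outcome of interest is the aggregate number of visits for MOVE! candidates who live within 40 miles of their VAMC". Section 3.2 has "The primary outcome will be VAMC-level aggregated number of MOVE! visits accrued within a six-month analysis period among candidates for MOVE", again limited to those within 40 miles. Being a candidate decides whose visits are counted; the number of candidates is not a divisor.

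The Aim 2 analysis is a "generalized linear mixed-effects model with visit counts and log link for primary outcome". On its terms: "Each model will include site as random intercepts and two indicators for tertiles as fixed effects". The LEAP indicator is added to these. Other variables, such as quarter, are permitted but not required. No offset is named, and the nearest thing to a size term is facility complexity in the covariate list. Aim 1 is to use similar models, with a post-dissemination indicator as the exposure.

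For site selection, Section 3.1 says that eligible sites are "characterized by tertile of performance with respect to aggregate visits (our primary implementation outcome").

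Elsewhere the scale has a denominator. On Figure 4, Section 2.0 says "The highest-ranked VAMC reported more than 70 MOVE! group visits per 100 candidate Veterans". The LEAP effect is to be "expressed as rate ratio for primary outcome". The power paragraph contrasts visit rates of 7 and 5, built on a per-participant average. Section 4.0 says "we anticipate a 20% improvement in the aggregate visit rates for MOVE! group".

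**The concern.** A count of visits is the number of candidates multiplied by visits per candidate. Only the second factor describes how well a program reaches its population. Three things follow if the count is used as written.

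- **Tertiles.** Ranking on the count mixes size with performance. A large program with weak uptake could be drawn as one of the two high performers in a cohort, whom Section 3.1 relies on to mentor the others. No model term can repair this, because selection comes before the analysis.
- **Estimate.** Growth or shrinkage in a site's candidate pool is recorded as a change in reach.
- **Reproducibility.** Two analysts following the text could build different endpoints and different tertiles, and a reader could not tell which rate the reported rate ratio refers to.

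**Working it through.** **The plan's own effect size.** 7/5 = 1.40 reproduces the stated rate ratio. Its source is an average of 4 visits in six months per participant, and the sample-size product gives every site the same 20 participants per quarter. The power scale therefore has a denominator and no variation in size. The endpoint in Section 3.2 has no denominator.

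**How the ranking can reverse (sizes assumed).** 4,000 candidates at 15 visits per 100 give 600 visits; 1,000 candidates at 50 per 100 give 500. The site with the lower rate ranks higher on the count.

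**How many sites change tertile.** Write log(count) = log(candidates) + log(rate). The documents give no distribution of candidates, so both SDs are assumptions: rate 0.5-0.7, candidates 0.3-0.7, log-normal and independent. As a rough check on the rate, if 10 and 70 visits per 100 in Section 2.0 bounded the central 95% of sites, the SD would be ln(70/10)/3.92 = 1.946/3.92 = 0.50.

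Simulation of 147 sites, 2,000 draws per setting, comparing count tertiles with rate tertiles:

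| Rate SD | Size SD | Share of log-variance due to size | Sites in a different tertile | Top count tertile not top by rate |
|---|---|---|---|---|
| 0.7 | 0.3 | 0.09/(0.09+0.49) = 0.16 | 23.5% | 17.7% |
| 0.5 | 0.7 | 0.49/(0.49+0.25) = 0.66 | 47.4% | 40.9% |

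A second set of assumptions (size CV 0.3-1.0, rate CV 0.4-0.6) gives 28-54% in a different tertile.

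**Constant size and the LEAP ratio.** Generalised least squares with a site random intercept and quarter effects: 147 sites, 9 quarters, 48 sites stepped in by sixes, true ratio 1.40, size CV 0.3-1.0. The mean estimate is 1.39-1.41 with or without the offset. With residual variance 0.04 the standard error is 0.0245-0.0247 without the offset and 0.0245 with it. With residual variance 0.10 it is 0.0383-0.0388 against 0.0381. The largest variance ratio in these runs is (0.0388/0.0381)² = 1.04.

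**Changing pools.** If a site's pool changes by a factor k, its count ratio is k times its rate ratio.

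- *Common drift, no quarter term, no offset, no true effect.* Number the quarters 0 to 8 (one unexposed quarter and eight steps, from the power paragraph). A site with c control quarters has mean control time (c − 1)/2 and mean LEAP time (c + 8)/2. The gap is 9/2 = 4.5 quarters whatever c is. Growth of g per quarter therefore gives a spurious ratio of about (1 + g)^4.5: 1.01^4.5 = 1.046 and 1.02^4.5 = 1.093. On the log scale these are 0.0448 and 0.0891, or 13% and 26% of ln(1.4) = 0.3365. The least squares calculation agrees (about 1.05 and 1.09) and returns 1.00 once quarter effects are included.
- *Site-specific change.* Quarter effects do not remove it. If it is unrelated to the randomised start, it adds variance and not bias. The size depends on a residual SD that the documents do not give, so no figure is offered.
- *Aim 1.* The exposure is an indicator for the period after dissemination, so a rise in candidate numbers around FY17 Q1 loads on it unless a trend term or an offset absorbs it. Neither is stated.

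**The case against.** The strongest reply is that a rate was meant all along. The Figure 4 title attaches the word aggregate to visits per 100, and Section 2.0 then describes those per-100 differences as variation in aggregate visits. Section 3.1 uses the same term for the tertiles, and the only ranking of VAMCs shown is per 100. This stands in part. The tertile problem rests on conflicting wording, so a reader should not infer that sites were certainly ranked by size. But Section 3.1 also identifies the ranking variable as the primary outcome, which Section 3.2 defines as a number, and nowhere is it said to be per candidate.

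A second reply is that visit counts may be person-level records, with the denominator built in. Section 3.2 does allow participant covariates, but its definition is aggregated to the VAMC. A third is that the text is an excerpt that points elsewhere for detail. That is fair, and a missing offset may be an omission and not a choice.

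A reader might also infer that facility size biases the LEAP effect. It does not: the site intercept and the within-site contrast absorb constant size, and random selection within tertiles is valid whatever variable forms them. Nor does it follow that the reported ratio is incomparable with the 20% target in Section 4.0. With a stable pool the count ratio equals the rate ratio. That target also covers the products and LEAP together, so it is not the LEAP contrast on either scale.

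**Conclusion.** The concern holds in this form. As written, the primary outcome is a count with no denominator and the model has no offset, while the rationale, power, effect measure and impact statements use rates. The passages need to be reconciled.

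If the count is used for the tertiles, about 23-47% of sites would be placed differently than on visits per candidate. This range rests wholly on assumed spreads of rate and size. For the LEAP estimate, constant size is harmless and costs little precision. The exposure is to change in the pool: noise from site-specific change, and a spurious ratio of about 1.05-1.09 under an assumed 1-2% common growth per quarter if the quarter term is omitted. The same growth could be mistaken for a product effect in Aim 1. The plan should be changed, but the Aim 2 comparison is not invalidated.

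**What to change.** 1. Define the primary outcome as MOVE! visits per candidate living within 40 miles during the analysis period.
2. Keep the log-link model and add log(number of such candidates) as an offset, in Aim 2 and in the Aim 1 time series. The rate ratio then has a named denominator, and drift in the pool is removed whether or not quarter is included.
3. State in Section 3.1 that tertiles are ranked each quarter on visits per 100 candidates, the Figure 4 metric. Where sites have already been selected, report which measure was actually used.

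The cost is wording plus one candidate count per site-period from the Corporate Data Warehouse. Figure 4 shows that a candidate denominator can be computed, and the 40-mile limit already applies to the outcome. No patients, visits or sites are added.

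### The six-month primary count is paired with an exposure that switches at one quarter, with no visible rule for windows spanning LEAP start and with calendar quarter optional; either gap can bias the LEAP rate ratio

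*Combined protocol and SAP*

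**What the plan says.** Section 3.2 (Key Variables & Analyses) defines the primary outcome as "VAMC-level aggregated number of MOVE! visits accrued within a six-month analysis period", counted among MOVE! candidates living near the site. In the Aim 2 model, exposure is binary and time-dependent: "a variable indicating the quarter at or beyond when the site is randomized to initiate LEAP". Site is a random intercept and performance tertile a fixed effect. Calendar time is optional: "The model can include other variables (e.g., quarter and participant covariates").

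The power paragraph of Section 3.2 assumes "randomization of 6 sites (2 sites per tertile) to LEAP every quarter over 8 quarters starting at Q1 of FY17", with one unexposed quarter. Section 3.0 describes 48 randomised sites, "with the remaining sites acting as controls"; the power paragraph counts 99 of these.

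Two statements bear on where windows fall. Section 3.1 says "The final three months of follow-up for the last cohort will occur in FY19Q1". For Aim 1 only, Section 3.2 uses LEAP-site data "up to the randomization time for sites randomized to LEAP". No such cut is stated for Aim 2.

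**The concern.** The outcome covers two quarters, but exposure changes at the start of one, and six sites change every quarter. Unless windows are tied to each site's start, every LEAP site has a window with one quarter before LEAP and one after. A binary code must call that window all control (if coded by its first quarter, a forward window) or all LEAP (if coded by its last quarter, a backward window). Either choice blurs the contrast.

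The optional quarter term is a second problem in the same model. In a stepped-wedge design, exposed time falls later than unexposed time, so any trend in visits is credited to LEAP when period is left out. A trend is plausible because the plan releases its core products to all sites in FY17.

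At stake are the size of the primary rate ratio and its interval and, if quarter is omitted, the validity of the test.

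**Working it through.** **Inputs from the plan.** Visits 7 vs 5 per six months; 8 cohorts of 6 sites starting FY17Q1 to FY18Q4; 99 never-randomised sites; one unexposed quarter (FY16Q4); follow-up to FY19Q1; 20 participants per site-quarter; within-site correlation 0.1; two-sided 0.05; 99% power at 1.4.

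**The plan's own figures.** 7/5 = 1.40. A standard stepped-wedge variance formula (48 sites, 9 periods, 20 per site-quarter, between-site variance 0.1 on the log-odds scale) gives 91.3% power at the tertiary odds ratio of 1.48, against the stated 91%. For the count at 1.4, Poisson variance gives about 100%, against 99%.

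**One straddling window.** Quarterly expectations are 2.5 (control) and 3.5 (LEAP). A half-exposed window expects 2.5 + 3.5 = 6, so its ratio to a clean control window is 6/5 = 1.20, not 1.40.

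**How many.** FY16Q4 to FY19Q1 is 10 quarters, so 9 overlapping six-month windows per site and 48 × 9 = 432 at LEAP sites. With forward windows, cohort k has k control-coded windows: 6 × (1 + … + 8) = 216, of which 48 (one per site) are half LEAP. With backward windows, 216 + 48 = 264 are coded LEAP, of which 48 are half control. Cohort 1 has no clean control window.

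**Expected estimate.** I took the expected generalised least-squares coefficient, (X′V⁻¹X)⁻¹X′V⁻¹y. Here y is the log mean of two adjacent quarterly rates, V has a site random intercept, and X has exposure plus window-start effects. Sites have equal volume, so tertile indicators are left out. The plan does not say what its 0.1 refers to, so three readings are shown: 0.1 between site totals, or 0.1 between participants, which gives 0.1/(0.1 + 0.9/20) = 0.69 or 0.1/(0.1 + 0.9/40) = 0.82 for site totals.

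| True effect | Coding | ρ = 0.1 | 0.69 | 0.82 |
|---|---|---|---|---|
| 1.40 at once | forward | 1.367 | 1.321 | 1.317 |
| | backward | 1.352 | 1.337 | 1.335 |
| | straddling windows excluded | 1.400 | 1.400 | 1.400 |
| 1.2 in first quarter, then 1.40 | forward | 1.356 | 1.325 | 1.322 |
| | straddling windows excluded | 1.372 | 1.362 | 1.361 |
| 1.0 in first quarter, then 1.40 | forward | 1.343 | 1.329 | 1.327 |
| | straddling windows excluded | 1.343 | 1.322 | 1.320 |

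Fractional coding (0, 0.5, 1) also returns 1.40 when the effect is immediate. On the log scale the forward loss is 1 − ln(1.367)/ln(1.4) = 7% to 1 − ln(1.317)/ln(1.4) = 18%. A Poisson log-link fit to expected counts with site fixed effects gives 1.310 (forward), 1.400 (excluded) and 1.399 (fractional).

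**Power and coverage.** Reading the plan's 99% as applying to the rate ratio, the implied SE is ln(1.4)/(1.960 + 2.326) = 0.0785. At 1.317, power is 94% and 95% interval coverage of 1.40 is 88%; at 1.367 they are 98% and 94%.

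**Quarter term omitted, forward windows.** With a true rate ratio of 1.00, visits rising 1% per quarter give 1.028 to 1.044 and 2% gives 1.056 to 1.090. With quarter effects, a 2% rise gives 1.00. With a true 1.40 and a 1% rise, the plan's forward coding gives 1.387 to 1.407, because the two errors offset. Correcting the windows alone gives 1.438 to 1.471.

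**Cost.** Relative to forward coding, the SE is 1.023 to 1.116 times as large with exclusion and 1.017 to 1.102 with fractional coding. With FY16Q3 added, the ratios against forward coding without that quarter are 1.003 to 1.013.

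**The case against.** The document is an excerpt. Figure 5, the trial-design diagram, is not shown, and the opening page points to a linked page for further analysis detail. Either may hold the rule. That stands, and it is why the window part of this point is conditional.

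A reader might infer that the plan does use calendar windows and so will understate LEAP. The documents do not support that. Section 3.1's follow-up statement for the last cohort fits six months counted forward from a site's own start. It does not, however, place windows before LEAP or at the 99 sites that never start.

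The power paragraph's closed quarterly participant cohorts also allow another reading: visits counted by entry cohort and coded by entry quarter. If the effect attaches to the entry cohort, forward coding returns exactly 1.40 and nothing needs removing. Fractional coding would then give 1.385 to 1.406, while exclusion still gives 1.40. Section 3.2's site-level definition leaves both readings open.

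An immediate full effect is a strong assumption. Section 2.1 (LEAP) puts planning in the early sessions, tests of change in the later ones, and describes change as incremental. With no first-quarter effect, forward windows have no bias to remove.

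Backward windows do worse under delay (1.21 to 1.26 with no first-quarter effect), but nothing readable suggests them, so those figures should carry little weight. A fit to the 48 LEAP sites alone gives a lower figure (1.26, forward), but Section 3.0 keeps the other sites as controls. Nor do the documents tie scale-up to a threshold on this rate ratio: Aim 3 assigns that to the formative and cost evaluations.

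None of this answers the optional quarter term.

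**Conclusion.** The point holds in two parts.

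- **Windows (conditional).** If windows follow calendar time, LEAP acts on site visits in its first quarter and quarter effects are fitted, a true 1.40 is estimated at about 1.32 to 1.37 with forward windows, the reading closest to Section 3.1. This is a fault of estimation: power stays at 94 to 98%, so it would be wrong to infer that the trial is underpowered. The loss shrinks as the effect is delayed and is absent under the entry-cohort reading.
- **Quarter term (not dependent on window placement).** Leaving calendar quarter out biases the rate ratio under any secular trend: about 1.03 to 1.09 with no LEAP effect and a rise of 1 to 2% per quarter. The trend sizes are illustrative assumptions.

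The direction is not fixed for the model as written. Without quarter effects, dilution and trend can cancel or the estimate can exceed the truth, so the two gaps should be closed together. The plan should be changed, but confidence is medium because the figure and linked page could not be read.

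**What to change.** 1. Make quarter (period) fixed effects mandatory in the Aim 2 primary model.
2. Anchor six-month windows to each site's LEAP start, with matching calendar windows at never-randomised sites. Exclude windows that straddle the start, or code them by fraction exposed (0, 0.5, 1). Do not do this without step 1, because the window correction alone overshoots (1.44 to 1.47 at +1% per quarter). State whether visits are counted by calendar time or by entry cohort; under the latter, exclusion is the safer of the two.
3. Include FY16Q3 and FY16Q4 so that cohort 1 has a clean six-month control window. Aim 1 already plans such data: "Data prior to launch of these products (FY17 Q1) will provide" its before period.

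The cost is SAP wording and quarterly dates from administrative data already in use. The SE rises about 2 to 12%, leaving power at 1.40 of about 97 to 99%. With FY16Q3 added it is only 0.3 to 1.3% above forward coding without that quarter. For forward windows, step 2 gains little if LEAP has no first-quarter effect. If Figure 5 or the linked page already anchors the windows, only step 1 and, if not already covered, step 3 remain.
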